8.0 Study Endpoints

8.1 Describe the primary and secondary study endpoints.

Primary Outcome/Endpoint: reduction in frequency and intensity of VMS subjective hot flashes that have been recorded on a paper diary for the duration of the study.

Title: SGB CA Study

Secondary outcomes/endpoint: Changes in the following measures from baseline, 3 months, 6 months:

Objective hot flashes as measured over a 24-hour period with a validated skin conductance monitor

Memory: Mini-Mental State Exam (MMSE)

Mood: Depression Anxiety and Stress Scale (DASS) and Center for Epidemiological Studies-Depression (CES-D)

Cognition: Neurocognitive testing: California Verbal Learning Test (CVLT),List A, List B, List A Short-Delay Free Recall, List A Short-Delay Cued, Recall, List A Long Delay Free Recall, Long Delay Cued Recall, Card Rotation Tests, Digit Span (Forward and Backward), Benton Visual Retention Test,(BVRT), Finding As, Brief Test of Attention (BTA) Numbers, Brief Test of Attention (BTA) Letters, Logical Memory Subtest of Wechsler Memory Scale, Revised (WMS-R/LM-R), Letter, Semantic and Phonemic Fluency) Baseline and 3 months only.

QOL: Functional Assessment of Cancer Therapy-Breast (FACT-B McCoy Female Sexuality Questionnaire (MFSQ)),

Sleep: Pittsburg Sleep Quality Inventory (PSQI), Actigraphy changes in sleep Quality

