9.0 Procedures Involved

9.1 Describe and explain the study design.

Title: SGB CA Study

We aim to conduct a randomized, single-site, sham-control clinical trial of SGB on VMS in 36 women with breast cancer on anti-estrogen therapy (18 per group). We will need to screen and enroll approximately 50 women to randomize 36 women. Some women may not qualify due to insufficient number of hot flashes or there may be some withdrawals. The primary entry criterion will be 28 or more moderate to very severe hot flashes per week. VMS will be measured by self-report on a written daily dairy over a 6-month period. Secondary outcomes include changes in mood, sleep, quality of life, memory performance with neurocognitive testing, and objective hot flashes measured by ambulatory monitoring (skin-conductance temperature monitoring) for 24 hours at baseline, three months and six months.

Randomization and Masking Procedures A computer-generated 1:1 block randomization scheme will be used to assign participants to receive either a SGB with bupivacaine or a sham injection with saline. Randomization will be performed by the injectionist immediately before the injection procedure by opening an opaque envelope to reveal the participant number and group assignment printed on an index card. Randomization assignment will be kept under lock and key. Participants and all other study personnel, including those who will perform follow-up evaluations, will be blinded to group assignment. The injectionist will not have access to the written VMS diaries until the conclusion of the study.

9.2 Provide a description of all research procedures being performed and when they are performed, including procedures being performed to monitor subjects for safety or minimize risks.

Screening Visit 1

Recording of Hot Flashes

After the participant has reviewed and signed the consent form, they will be interviewed to determine if they are a candidate for the study. We will ask them to provide information about themselves and their medical history. A member of the study team will administer the Depression Anxiety and Stress Scale (DASS) to ensure that participants are not suffering from extreme anxiety or depression. If they are found to have any of these conditions and meet the exclusion criterion, they will not qualify for our study and will be referred to a mental health provider.

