11.0 Data and Specimen Management

11.1 Describe the data analysis plan, including any statistical procedures.

Subjective VMS: As described in the determination of eligibility based on VMS entry criteria section for six months following the intervention, intensity of daytime VMS will be calculated as follows: Intensity = Frequency*Severity = [(frequency of mild*1)+(frequency of moderate*2)+(frequency of severe*3)+(frequency of very severe*4)] and used as a secondary endpoint. Frequency of night sweats will also be recorded daily via self-report the following morning. Baseline VMS frequency will be calculated as the mean of the daily count totals on diaries during the first two screening weeks. VMS frequency at Months 1 to 6 will be calculated as the mean of the daily count totals reported for the 30 days before each visit.

Objective VMS: At baseline, and the 3- and 6-month post-intervention visits, participants will complete a second measure VMS objectively using the ambulatory sternal skin conductance monitor (Biolog Model 3991 x/2-HFI). Raw objective hot flash data will be analyzed by a combination of automated computer software and two trained data coders. According to standard procedures, once an objective hot flash will be coded, no other VMS will be coded for the next 15 minutes. Data will be independently double-scored and double-entered into the database by coders blinded to treatment assignment. Participant sensitivity to objective HF will be calculated by dividing the total number of true positive hot flashes (i.e., objectively determined hot flashes that were subjectively detected) by the sum of the total number of objectively measured hot flashes (i.e., true positives and false negatives). Primary outcome measures will be total objective and subjective hot flashes in a 24-h period, during waking hours, and during sleeping hours.

Title: SGB CA Study

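### Diary intensity is primary in section 8.1 but secondary in 11.1, no rule says which diary result decides the trial, and a loosely worded monitor sentence adds a second apparent conflict

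*Combined protocol and SAP*

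**What the plan says.** Section 8.1 gives the primary endpoint as "reduction in frequency and intensity of VMS subjective hot flashes that have been recorded on a paper diary for the duration of the study". Among the secondary outcomes it lists "Objective hot flashes as measured over a 24-hour period with a validated skin conductance monitor".

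Section 9.1 agrees on the monitor data: "Secondary outcomes include changes in mood, sleep, quality of life, memory performance with neurocognitive testing, and objective hot flashes measured by ambulatory monitoring". On the diary it says only "VMS will be measured by self-report on a written daily dairy over a 6-month period", without naming frequency or intensity.

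Section 11.1, under Subjective VMS, defines a severity-weighted intensity score for daytime VMS, "and used as a secondary endpoint". Night sweats are handled in a separate sentence. Diary frequency is defined but not ranked: "VMS frequency at Months 1 to 6 will be calculated as the mean of the daily count totals", taken over the 30 days before each visit.

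The Objective VMS paragraph of 11.1 ends: "Primary outcome measures will be total objective and subjective hot flashes in a 24-h period, during waking hours, and during sleeping hours".

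For the tests, 11.1 applies one mixed-model approach to all primary and secondary outcomes, each two-sided at .05. Section 11.2 claims at least 80% power with 18 per group for the Treatment by Time interaction and names no outcome. The hypothesis in 1.1 covers frequency and intensity, subjective and objective, without ranking them.

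**The concern.** The same diary measure has two ranks in current text. Someone following 8.1 would judge the trial on frequency and intensity; someone following 11.1 would treat intensity as supportive. The plan has no success rule, testing order or multiplicity adjustment to settle the matter. If the two measures disagree, the same data can be reported as positive or negative, and the choice can be made after the results are seen.

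The study calls itself a pilot, which lowers the stakes. It is nonetheless randomized and sham-controlled, tests at .05, claims a stated power, and is meant to support a larger grant application. Which result counts should be fixed beforehand.

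**Working it through.** **1. The labels side by side**

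| Measure | 8.1 | 9.1 | 11.1 |
|---|---|---|---|
| Diary frequency | primary | not named | defined, not ranked |
| Diary intensity | primary | not named | secondary (daytime score) |
| Objective hot flashes | secondary | secondary | in the list called primary |

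The second row is a reversal. The third is a conflict on its face. Frequency is primary in 8.1 and demoted nowhere.

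**2. The plan's own figure.** The 80% in 11.2 cannot be reproduced, because no outcome, effect size, standard deviation, within-subject correlation or number of time points is given. It can only be back-solved. On a single two-group contrast with 18 per group at two-sided .05, 80% power needs a standardized difference of (1.960 + 0.842) × √(2/18) = 2.802 × 0.3333 = 0.934 (0.961 with the noncentral t). The plan does not say which outcome this would refer to.

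**3. Correlation between the two diary measures.** The documents give none, so it is assumed. Intensity is 1×mild + 2×moderate + 3×severe + 4×very severe, that is, frequency times mean severity. If mean severity S is independent of frequency F, with coefficients of variation cS and cF, then r = 1/√(1 + cS²/cF² + cS²). Assume mean severity 2.3 with a between-woman SD of 0.2 to 0.6, and cF of 0.4 to 0.8:

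- Low end: cS = 0.6/2.3 = 0.261, cF = 0.4, so r = 1/√(1 + 0.425 + 0.068) = 0.82.
- High end: cS = 0.2/2.3 = 0.087, cF = 0.8, so r = 1/√(1 + 0.012 + 0.008) = 0.99.

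I use r = 0.9 to 0.95 and take it as the correlation of the test statistics.

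**4. How often the two rules disagree.** Assume each measure has 80% power on a single contrast. The chance that both are significant is the bivariate normal probability Φ₂(0.842, 0.842; r). Judging by frequency alone and requiring both differ only when frequency succeeds and intensity fails, with probability 0.80 − Φ₂.

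| r | Both significant (joint power) | Rules disagree |
|---|---|---|
| 0.90 | 0.750 | 0.800 − 0.750 = 0.050 |
| 0.95 | 0.765 | 0.800 − 0.765 = 0.035 |

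Sensitivity: at r = 0.7, joint power is 0.713 and the rules disagree in 0.087 of trials.

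**5. Sample size if both must succeed.** At r = 0.9, 80% joint power needs 84.3% power per measure. The multiplier on n is 1.121, so 18 × 1.121 = 20.2, or 21 per group.

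**The case against.** **The intensity labels may describe different variables.** The secondary score in 11.1 is for daytime VMS, 8.1 sets no daytime limit, and section 3.2 has women rate every hot flash and night sweat. A daytime score could therefore be secondary beside an all-day primary. This is possible but weak: 11.1 gives the plan's only intensity formula, so on this reading a primary endpoint would have no definition. What stands is that the scope of intensity has to be settled together with its rank.

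**The monitor sentence is probably only loose wording.** It closes the monitor paragraph, after a sensitivity calculation that counts "objectively determined hot flashes that were subjectively detected" and so needs self-report during monitoring. Its 24-hour window matches the monitor session, whereas the diary frequency averages two weeks at baseline and 30 days afterwards. Sections 8.1 and 9.1 both rank objective hot flashes secondary. I accept this as the more natural reading.

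A reader might go further and infer six trial primaries (two types of count over three windows), with an inflated false-positive rate because any one could carry the trial. The documents do not support that: the sentence's place points to monitor variables, and no passage says that one significant primary is enough.

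**It is a pilot of 36 women.** This stands as a reason to rate the point below the most serious. It does not reconcile the labels.

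**The arithmetic is not the planned test.** True: 11.2 powers a Treatment by Time interaction, and the figures above use a single contrast. They show scale only.

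**Conclusion.** The plan is wrong as written on the rank of diary intensity, and it lacks a rule for which diary result decides the trial. The monitor sentence is a probable wording fault that needs a qualifier; it is not evidence that objective hot flashes were made primary. The documents do not establish an inflated error rate: if both diary measures must succeed, the cost is power.

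The practical size is modest: different verdicts in about 5% to 3.5% of trials, and joint power of about 75% to 76%. This rests on 80% power per measure on a single contrast and a correlation of 0.9 to 0.95, neither of which the documents give. The contradiction itself depends on no calculation. It should be fixed before unblinding, but in a small pilot it is not a critical defect.

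**What to change.** Use one hierarchy in 8.1 and 11.1, by either route:

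- **(a) Single primary.** Make diary VMS frequency the only primary. Test it once at two-sided .05 by the between-arm difference in change from baseline in a mixed model, averaged over Months 1 to 6 or over another period fixed before unblinding. Intensity becomes secondary in 8.1 as well.
- **(b) Co-primaries.** Keep frequency and intensity as in 8.1, require both to reach p ≤ .05, delete the phrase in 11.1 that calls intensity secondary, and restate the joint power.

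In either case:

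- State whether intensity covers daytime only or all VMS.
- Open the monitor sentence in 11.1 with *Main monitor-derived (secondary) measures will be*, keeping its list.
- Name in 11.2 the outcome and contrast to which the 80% power applies.

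The cost is wording only, with no new visits or data. Under (a), intensity loses primary status. Under (b), the stated power is lower, or at r = 0.9 about 21 per group would be needed in place of 18, if 18 gives exactly 80% for each measure.

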1.0 Objectives

1.1 Research Aims:

Vasomotor symptoms (VMS) affect up to 65% of breast cancer survivors and negatively impact their quality of life. VMS in African American and Latino women are significantly more severe as compared to Caucasian women. Symptom management should be a priority in Women's Health research. Few effective treatments for VMS are available. Stellate ganglion blockade (SGB) with local anesthetic, previously performed for chronic pain indications, has shown promise as a treatment for women with VMS in previous clinical trials, but has not been investigated in women with breast cancer receiving anti-estrogen therapy in a randomized, sham-control study.

We aim to evaluate the benefit of SGB in symptomatic women with breast cancer seeking relief from moderate to very severe VMS that are adversely affecting health and wellbeing.

Scope: Women with breast cancer on Tamoxifen, aromatase inhibitors or SERMs with moderate to very severe VMS will be enrolled as participants in this study.

Hypotheses:

The frequency and intensity of subjective and objective VMS will be significantly lower in women randomized to active SGB as compared to sham controls. Mood, memory, cognition, sleep, and quality of life will all be improved in the treatment group as compared to the sham-control group.

Specific Goals and Objectives:

Goal 1: To determine the effect of stellate ganglion blockade (SGB) for reducing subjective and objective VMS in women with breast cancer on tamoxifen, AIs, or SERMs

Goal 2: To evaluate the effect of SGB on mood, memory, cognition, sleep and quality of life in women with breast cancer on tamoxifen, AIs, or SERMs.

Goal 3: Using the results of this pilot study, we plan to submit an R01 grant to the National Cancer Institute for a larger scale study.

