Baseline characteristics: (e.g., sociodemographic variables, primary and secondary outcomes) will be compared between treatment groups using t-tests or chi-square tests for categorical variables. Multiple types of measurement outcomes (frequencies, counts, continuous and incidence outcomes) will be collected in this study. We will conduct intent-to-treat (ITT) analyses for all primary and secondary outcomes using a series of generalized mixed-effects regressions as described below. All statistical tests will be two-sided with significance set at $p \leq .05$. SAS statistical software version 9.2 (SAS Institute Inc., Cary, NC, USA) will be used for statistical analyses. In preliminary analysis, the distributional aspects of the variables under consideration will be examined through descriptive statistics. These statistics will include measures of location (mean, median, quartiles) and measures of dispersion (range, standard deviation, variance) for continuous variables and frequencies of the levels of categorical variables. These measures will also assist with a data cleaning/screening procedure to eliminate any possible copying, handling, recording or measurement errors.

In addition to the features described above, the dependence of outcome measures will need to be properly accounted for in the data analysis as measures will be made at multiple times for the same participant. Consequently, these observations tend to be correlated and require statistical techniques that can properly account for the correlation in order to draw valid inference. Our general approach for analyzing these multiple types of data in this trial will be the Generalized Linear Mixed-Effect Models (GLMM). These models can accommodate a wide range of outcomes including normal, binary, ordinal, and Poisson outcomes, while taking into account correlations from within-subject observations. To study the changes in outcomes over time and to evaluate group differences in these changes, we will construct GLMM models. The main independent variables in statistical model specifications typically include the group indicator, dummy variables for time, and the interactions between them, after controlling for observed and relevant covariates. By properly constructing GLMMs, a wide range of scientific hypotheses can be tested, including cross-sectional differences among groups, the effect of treatment over time and differences between groups over time.

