Data will be analyzed using the PROC MIXED, PROC GLIMMIX and PROC NLMIXED in SAS statistical software version 9.2. For the correlation between changes in objective VMS and changes in memory performance, we propose to examine the correlation between frequency of total objective VMS and verbal learning by conducting Pearson correlations to examine associations between changes in cognitive performance and changes in VMS. We will conduct partial correlations to examine whether these associations remained significant after controlling for changes in sleep quality (PSQI and actigraphy-based measures).

11.2 Provide a power analysis, if necessary.

A sample size of 18 in each treatment group will provide at least 80% power to test the two-way interaction between Treatment and Time with a significance level set at 0.05.

Title: SGB CA Study

We will need to screen and enroll approximately 50 women to randomize 36 women. Some women may not qualify due to insufficient number of hot flashes or there may be some withdrawals.

11.3 Describe the steps that will be taken to secure the data to maintain confidentiality (e.g., training, authorization of access, password protection, encryption, physical controls, certificates of confidentiality, and separation of identifiers and data) during storage, use, and transmission

Research files and case report forms will be stored in the research offices of [name] and will be kept in locked offices with access only to the research team. Wherever possible, subject data will be stored using only the study ID. Measures will be taken to protect all personal information and data, including keeping all data sheets under lock and key and entering data into a database that requires login identification and a password made available only to immediate study personnel. The entire study team has taken the CITI training and is familiar with confidentiality requirements and procedures.

Downloaded data from the Biolog hot flash monitor and the actigraph watch will be processed, stored, and analyzed in password-protected network at the University of Illinois in Chicago of [name]. Data related to cognitive assessments will be stored and analyzed at the University of Illinois at Chicago in [name] lab.

11.4 Describe any procedures that will be used for quality control of collected data

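### The planned correlations between change in objective hot flashes and change in verbal learning adjust for sleep but not for treatment arm, so two parallel treatment effects could look like a link between the measures.

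*Combined protocol and SAP*

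**What the plan says.** For the relation between hot flashes and memory, section 11.1 states: "we propose to examine the correlation between frequency of total objective VMS and verbal learning". The method is "conducting Pearson correlations to examine associations between changes in cognitive performance and changes in VMS". One adjustment follows: "We will conduct partial correlations to examine whether these associations remained significant after controlling for changes in sleep quality", measured by the PSQI and actigraphy.

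Treatment arm does appear in section 11.1, but in the description of the mixed models for the outcomes: "The main independent variables in statistical model specifications typically include the group indicator, dummy variables for time, and the interactions between them". Nothing carries that term into the correlations. No stratified or within-arm correlation is described anywhere.

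Section 1.1 expects objective VMS to be lower in the active arm, and also that "Mood, memory, cognition, sleep, and quality of life will all be improved in the treatment group as compared to the sham-control group". Section 2.2 reports that in the team's earlier randomized trial both objective hot flashes and verbal learning improved after SGB, and that such benefits were not seen after sham.

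**The concern.** A correlation computed over two arms mixes two sources of covariation: how the changes move together among women in the same arm, and how the arm means differ. If SGB reduces hot flashes and separately improves verbal learning, the active arm sits at one corner of the scatter plot and the sham arm at the opposite corner. A line through both clouds then has a slope even if each cloud is round. The coefficient cannot distinguish a VMS-memory association from two parallel treatment effects.

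Parallel effects are credible here, because section 2.3 says that the mechanism of SGB is not fully understood and lists several possible central actions. Section 1.1 says the results will support an application for a larger study, so an apparent link between hot flashes and memory could be carried forward on weak evidence.

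**Working it through.** **Inputs from the documents.** 18 women per arm (sections 9.1 and 11.2); 1:1 allocation (9.1); two-sided tests at .05 (11.1); arm not among the variables partialled out (11.1). Cognitive testing is at baseline and 3 months only (8.1), so the change runs over that interval.

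**Inputs that must be assumed.** No SD or standardised effect is given for objective VMS or verbal learning. Let d1 and d2 be the arm differences in change on the two measures, in within-arm SD units. A range is used. Changes are taken as normal, with zero correlation inside each arm.

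**The plan's own figure.** Section 11.2 says: "A sample size of 18 in each treatment group will provide at least 80% power to test the two-way interaction between Treatment and Time". This cannot be reproduced without an effect size. Inverted for a simple contrast of change scores, the detectable difference is (1.960 + 0.842) × √(2/18) = 0.93 SD (0.96 with the t distribution). This is only a guide to where in the range the trial's assumptions may lie. No power is stated for the correlation.

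**Correlation created by the arm means.** With equal arms and no within-arm link, the correlation of each measure with arm has size (d/2)/√(1 + d²/4). The pooled correlation is the product of the two:

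|r| = (d1·d2/4) / √[(1 + d1²/4)(1 + d2²/4)]

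For d1 = d2 = 1.0: 0.25/√(1.25 × 1.25) = 0.20. For 1.5 and 1.0: 0.375/√(1.5625 × 1.25) = 0.27. With 36 women, significance requires |r| of at least 0.329.

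**Why adjusting for arm removes it.** The numerator of the partial correlation is r(VMS, memory) − r(VMS, arm) × r(memory, arm). In this setting the first term equals the product, so the population partial correlation is zero.

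**Rejection rates, no within-arm link** (simulation, at least 40,000 trials per row):

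| Assumed effect, VMS/memory (SD) | Expected \|r\| | Both arms together, n = 36 | Arm partialled out, n = 36 | Both arms together, n = 24 |
|---|---|---|---|---|
| 1.0/0 | 0 | 5% | 5% | 5% |
| 0.5/0.5 | 0.06 | 6% | 5% | 6% |
| 0.8/0.5 | 0.09 | 8% | 5% | 7% |
| 0.8/0.8 | 0.14 | 13% | 5% | 10% |
| 0.93/0.93 | 0.18 | 18% | 5% | 14% |
| 1.0/0.8 | 0.17 | 16% | 5% | 12% |
| 1.0/1.0 | 0.20 | 22% | 5% | 16% |
| 1.5/1.0 | 0.27 | 37% | 5% | 26% |

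The last column assumes that 24 women, 12 per arm, have both change scores. With 15 per arm, suggested by the total of 30 in section 21.3, the 0.93/0.93 case gives 16%.

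**Does the planned sleep adjustment help?** At 0.93/0.93 with 18 per arm, the sleep-adjusted test rejects in 18%, 17% and 15% of trials when the arm difference in sleep change is 0, 0.5 and 0.8 SD. Sleep change is a weak stand-in for arm.

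**Power given up if the link is real.** Assume VMS change fully mediates the memory effect, with a within-arm correlation of 0.3 in size and 18 per arm. For a 1.0 SD effect on VMS, power is about 52% with arms together and 42% to 43% with arm partialled out. For 1.5 SD it is about 61% and 43%.

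**The case against.** The strongest reply has four parts.

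- **The plan never says that the arms are pooled.** True. Pooling is inferred from a Pearson correlation whose only named control is sleep. A reader might conclude that the sponsor has declared a pooled analysis; the text supports only that arm is not mentioned. An analyst following the text would still leave arm out.
- **Rejection need not be an error.** Section 11.1 speaks of examining associations and makes no mediation claim. When both arm means shift, the marginal correlation really is non-zero, so rejecting zero marginal correlation is correct. This stands. The rates above are error rates only for the question of whether the two changes are related apart from treatment. That is the question a mechanistic reading needs.
- **The large rates need large effects on both measures.** This also stands. A reader might infer that the test misleads whenever SGB works. It does not: an effect on VMS alone leaves the rate at 5%, and 0.5 SD on both gives only 6%. Sections 9.2 and 12.3 also allow women to stay in the trial without cognitive testing, so 36 is a ceiling, and fewer evaluable women means lower rates.
- **Adjusting for arm discards real signal under mediation.** It does cost power, as shown. But the between-arm part of the covariation is exactly the part that cannot separate mediation from parallel effects. A genuine link should also show among women in the same arm.

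**Conclusion.** The point holds as a limited one. As written, the correlation analysis can show a VMS-memory association that comes wholly from treatment effects on both measures, and the planned sleep adjustment does not prevent this. With no within-arm link and 18 per arm, the chance of a significant result runs from about 6% at 0.5 SD on both measures to 37% at 1.5/1.0 SD. It is about 18% at the 0.93 SD that would match the stated power for a simple change-score contrast. All these effect sizes are assumptions, and the documents do not show which applies.

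A reader might take this as a flaw in the trial's evidence on efficacy, or as a sign that any observed link would be false. Neither follows. The outcome models in section 11.1 include arm. The correlation is listed neither among the goals and hypotheses in section 1.1 nor among the endpoints in section 8.1; in effect it is exploratory. A link that persists after adjustment for arm would not be explained by the difference in arm means.

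**What to change.** In section 11.1, before unblinding:

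1. Add treatment arm to the variables partialled out or, equivalently, regress change in verbal learning on change in objective VMS with arm in the model. Present the result with and without change in sleep quality.
2. State that any mechanistic statement will rest on the arm-adjusted estimate, and show the estimate within each arm.
3. Report the unadjusted Pearson coefficient as descriptive, with the number of women who have both change scores.

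This needs a sentence or two of text and one extra variable in the code. Visits, data collection and sample size do not change. The statistical cost is one degree of freedom, plus roughly 10 percentage points of power in the 1.0 SD mediation example above and more if the VMS effect is larger.
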